7.2.4 Neurological Examinations

Complete and abbreviated neurological examination will be conducted by the investigator or designee during the study as outlined in [Table 1](#) and [Table 2](#). A complete standard of care

ZX008 (Fenfluramine Hydrochloride)**ZX008-1601 Clinical Study PA 4.0 (Japan) 25 July 2022**

neurological examination for each subject will be performed and will cover the following: cranial nerves, muscle strength and tone, reflexes, coordination, sensory function, and gait. An abbreviated neurological follow-up examination for each subject will evaluate any symptoms or systems found to be abnormal and unstable or potentially unstable that might evolve during study treatment, or to investigate any reported or observed AEs.

Any unfavorable findings not present at screening, or worsened from the baseline assessment and considered by the investigator as clinically significant, occurring at any point in the study will be documented in the eCRF as an AE.

7.2.5 Vital Signs (Including Height and Weight)

Height, weight, and vital signs (blood pressure, heart rate, temperature, and respiratory rate) will be documented for subjects during study as outlined in [Table 1](#) and [Table 2](#).

7.2.6 Laboratory Measurements

Laboratory safety parameters will be analyzed using standard validated methods.

The following parameters will be assessed by the laboratory as described in [Table 1](#), [Table 2](#) and [Table 10](#):

- Hematology: hemoglobin, hematocrit, erythrocyte mean corpuscular volume, leukocytes, mean corpuscular hemoglobin, mean corpuscular hemoglobin concentration, neutrophils, lymphocytes, monocytes, eosinophils, basophils and platelets
- Blood Biochemistry: albumin (ALB), alkaline phosphatase (ALP), alanine aminotransferase (ALT; SGPT), aspartate aminotransferase (AST; SGOT), bicarbonate, blood urea nitrogen (BUN), calcium (Ca), carbon dioxide (CO₂), chloride (Cl), creatinine, creatine kinase, gamma-glutamyl transferase (GGT), glucose, lactate dehydrogenase (LDH), phosphorus, potassium (K), sodium (Na), total bilirubin, direct bilirubin, total cholesterol, total protein, triglycerides, uric acid, eGFR.
- Tests of growth and precocious puberty: Growth hormone (GH), insulin-like growth factor-1 (IGF-1), prolactin, Luteinizing Hormone (LH), Follicle Stimulating Hormone (FSH), testosterone, estradiol, thyroid function (T₃, T₄, and thyroid stimulating hormone [TSH]),
- Immunoglobulin (IgG, IgA, IgM)
- Epilepsy genotype panel
- Coagulation: Prothrombin time (PT)/International normalized ratio (INR), activated partial thromboplastin time (PTT)
- Whole blood cannabidiol
- Urinalysis: analysis for pH, glucose, ketones, nitrite, protein, bilirubin, urobilinogen, leukocyte esterase, and occult blood. Microscopic analysis will be performed for blood, all cell types, and casts.
- Urine or serum pregnancy test: Urine or serum pregnancy testing will be performed in

ZX008 (Fenfluramine Hydrochloride)
ZX008-1601 Clinical Study PA 4.0 (Japan) 25 July 2022

female subjects of childbearing potential.

- Urine or serum THC panel
- The investigator will receive the laboratory report from the central laboratory. After reviewing the report and evaluating any results that are outside the normal range for clinical significance, the investigator must sign and date the laboratory report in a timely fashion.

Tests resulting in abnormal laboratory values that have been classified by the investigator as abnormal, clinically significant should be repeated as soon as possible after receiving the laboratory report to rule out laboratory errors.

At Screening, any laboratory values that deviate from the reference ranges that are not exclusionary and are considered by the investigator as clinically relevant must be documented on the medical history form of the eCRF. Any deviation outside of the reference range considered by the investigator as clinically significant (ie, classified as an abnormal, clinically significant value) at any visit after screening will be documented in the eCRF as an AE (see [Section 9](#)).

7.2.7 Plasma Sample for Concomitant Antiepileptic Drug(s)

Plasma samples to ensure that concomitant AEDs dosing is within an acceptable range will be conducted during the study as outlined in [Table 1](#) and [Table 2](#). All samples will be analyzed at study end and do not constitute safety assessments. (Importantly, plasma samples for concomitant AEDs can be performed at any time if considered clinically indicated. In these instances results will be provided to the unblinded Medical Monitor and discussed with the Principal Investigator.)

7.2.8 Electrocardiograms

Twelve-lead ECGs will be conducted during study as outlined in [Table 1](#) and [Table 2](#) after the subject has been in the supine position resting for ≥ 5 minutes. Heart rate, PR duration, QRS duration, QT duration, QTcF (Fridericia's correction formula), and the investigator's overall interpretation will be recorded.

7.2.9 Doppler Echocardiography

Doppler echocardiography will be conducted at a facility with experience for the subject's age during study as outlined in [Table 1](#) and [Table 2](#). Doppler echocardiography uses ultrasound technology to examine the heart or blood vessels. An ECHO uses high frequency sound waves to create an image of the heart while the use of Doppler technology allows determination of the speed and direction of blood flow by utilizing the Doppler effect. Predetermined standard guidelines on the proper evaluation of certain measurements, as well as abnormality thresholds, were constructed by the sponsor's ICAB prior to study initiation. These thresholds are provided in [Table 9](#) and [Table 11](#). A manual of proper ECHO technique for sites is provided in a separate document.

7.2.10 Behavior Rating Inventory of Executive Function (BRIEF)

The Behavior Rating Inventory of Executive Function (BRIEF) is a parent or teacher report

ZX008 (Fenfluramine Hydrochloride)
ZX008-1601 Clinical Study PA 4.0 (Japan) 25 July 2022

measure designed to address the multidimensional nature of the executive function construct and will be used to assess the effects of ZX008 on cognition. The BRIEF assesses eight theoretically and statistically derived subdomains of executive function. It was designed to be used for a wide range of childhood disorders in order to augment traditional clinic-based assessments, and to provide an increased level of ecological validity for clinical assessments (Rabbitt, 1997). Age-appropriate versions of the BRIEF (BRIEF-P: 2 to 5 year olds; BRIEF: 6 to 18 year olds; BRIEF-A: 19 to 35 year olds), will be conducted according to the schedule in Table 1.

7.2.11 Tanner Staging

Tanner Staging (Appendix 5) will be assessed for subjects >7 to 18 years old during the study as outlined in Table 1 and Table 2. Conceptually, pubertal maturation can be described in terms of sequence, timing, and tempo. Puberty consists of a series of predictable events, and the sequence of changes in secondary sexual characteristics has been categorized by several groups. The staging system used most frequently was published by Marshall and Tanner (1969, 1970) and the sequence of changes are commonly referred to as 'Tanner stages'.

7.2.12 Columbia-Suicide Severity Rating Scale

C-SSRS (Appendix 2) will be assessed during study as outlined in Table 1 and Table 2. The C-SSRS is a validated rating scale that assesses suicidal behavior and ideation. The scale is used to assess and track suicide events and provides a summary measure of suicidal tendency. Age and intellectual development appropriate versions of the C-SSRS (Baseline/Screening and Since Last Visit) will be used in this study.

Subjects who are younger than 7 years chronologically, or who are judged by the investigator not to have the mental capacity to understand the questions as specified on the C-SSRS, will not complete the rating. The investigator should use his/her judgment to substitute intellectually-appropriate questions to probe the tendency for self-harm.

7.3 PHARMACOKINETIC ASSESSMENTS

Blood samples for PK assessments of fenfluramine and its metabolite (norfenfluramine) will be obtained from all subjects via an indwelling cannula or by venipuncture.

Blood samples for PK assessment (2 mL) will be obtained at the following time points:

- Part 1 Study Day 43: within 1 hour prior to the morning dose, and 1 (\pm 15 min), 2 (\pm 15 min), and 4-6 hours after the morning dose.

A total of 4 PK samples will be drawn for each subject for a total of approximately 8 mL of blood.

When blood draws for PK coincide with other assessments, the PK draws take precedence.

The procedure for the collection and handling of PK samples is outlined in a separate study manual.

7.4 EPILEPSY GENOTYPE PANEL

Optional blood samples for genetic analysis are being collected for a comprehensive analysis for a broad epilepsy gene panel that will be analyzed at the end of the study to investigate

ZX008 (Fenfluramine Hydrochloride)

ZX008-1601 Clinical Study PA 4.0 (Japan) 25 July 2022

genetic characteristics of study responders and non-responders. Whole genome sequencing is not being performed. Testing is restricted to a 377 childhood epilepsy gene panel; thus, the risk of revealing clinically relevant or medically actionable incidental findings is low. Samples may be retained for up to 24 months after the end of the study.

The field of genetics related to epileptic encephalopathies are developing rapidly, thus, in the event that new theories emerge on the genetics associated with LGS, the retained samples might be used to investigate this genotype in the study population. Results of genetic testing will only be provided upon written request; therefore, unless required by law individual results of genotyping will not be disseminated outside of the Sponsor, including to the study site. Genotyping samples will be double-coded (pseudonymized) so that it is impossible to trace back the personal identifying information from the sample number.

7.5 APPROPRIATENESS OF MEASUREMENTS

All of the variables assessed are standard tests or procedures that are commonly used in studies of this type.

ZX008 (Fenfluramine Hydrochloride)
ZX008-1601 Clinical Study PA 4.0 (Japan) 25 July 2022

8. ADVERSE EVENTS

8.1 DEFINITIONS

8.1.1 Adverse Events

According to ICH guidelines, an AE is any untoward medical occurrence in a patient or clinical investigation subject administered a pharmaceutical product and which does not necessarily have a causal relationship with this treatment. An AE can, therefore, be any unfavorable and unintended sign (including an abnormal, clinically significant laboratory finding), symptom, or disease temporally associated with the use of a medicinal (investigational) product, whether or not considered related to the medicinal (investigational) product. The period of observation for adverse events extends from the time the subject gives informed consent until the end of study.

Adverse events may include:

- Exacerbation (ie, an increase in the frequency or severity) of a pre-existing condition. Illness present before study entry should be recorded in the medical history section of the eCRF and only be reported as an AE if there is an increase in the frequency or severity of the condition during the study. Exacerbation of seizures is considered an AE if there was an increase in frequency beyond the subject's typical pre-study fluctuations, or in the event that seizures lengthen in duration in a clinically meaningful way compared with baseline, or if a new seizure type emerges.
- A clinical event occurring after consent but before IMP administration.
- Intercurrent illnesses with an onset after administration of IMP.

Adverse events do not include:

- Medical or surgical procedures (the condition that leads to the procedure is the AE, eg, tonsillitis is the AE if a tonsillectomy is performed)
- Situations where an untoward medical occurrence has not taken place. For example:
 - Planned hospitalizations due to pre-existing conditions, which have not worsened.
 - Hospitalizations that occur for procedures not due to an AE (eg, cosmetic surgery).
 - Hospitalizations for a diagnostic procedure where the hospital stay is less than 24 hours in duration or for normal management procedures (eg, chemotherapy).

For laboratory safety parameters, any instances of absolute values being outside the reference range or changes at any visit after study start that are considered by the investigator as clinically significant must be recorded in the eCRF as AEs. In addition, at the investigator's discretion, any changes or trends over time in laboratory parameters can be recorded in the eCRF as AEs if such changes or trends are considered to be clinically relevant, even if the absolute values are within the reference range.

Laboratory findings do not need to be reported as AEs in the following cases:

ZX008 (Fenfluramine Hydrochloride)
ZX008-1601 Clinical Study PA 4.0 (Japan) 25 July 2022

1. Laboratory parameters are already beyond the reference range, unless a further increase/decrease can be considered an exacerbation of a pre-existing condition.
2. Abnormal laboratory parameters caused by mechanical or physical influences on the blood sample (eg, hemolysis) and flagged as such by the laboratory in the laboratory report.
3. Abnormal parameters that are obviously biologically implausible (eg, values that are incompatible with life).
4. An abnormal laboratory value that cannot be confirmed after a repeated analysis, preferably in the same laboratory (eg, the previous result could be marked as not valid and should not necessarily be reported as an AE).

8.1.2 Serious Adverse Events

A serious adverse event (SAE) is defined as any untoward medical occurrence that at any dose:

1. **Results in death** – The event must be the cause of death for the SAE to meet this serious criterion.
2. **Is life-threatening** – The term “life-threatening” refers to an event in which the subject was at risk of death at the time of the event; it does not refer to an event that hypothetically might have caused death if it had been more severe.
3. **Requires in-patient hospitalization or prolongation of existing hospitalization** – The sponsor considers “hospitalization or prolongation of existing hospitalization” for at least 24 hours as the defining criterion for an SAE. Hospital admissions for planned surgery or for normal disease management procedures (eg, chemotherapy) are not considered as defining criteria for SAEs.
4. **Results in persistent or significant disability or incapacity.**
5. **Is a congenital anomaly or birth defect.**
6. **Is medically significant** – A medically significant event is defined as an event that does not meet any of the other 5 SAE criteria, but which is judged by a physician to potentially jeopardize the subject or require medical or surgical intervention to prevent one of the above outcomes listed as an SAE criterion. Anaphylaxis that is successfully treated by administration of epinephrine prior to other sequelae is an example of a potentially medically important event.

The most important term should be selected as the criteria for the SAE. Medically significant should be used when none of the other terms apply.

Suspected Unexpected Serious Adverse Reactions (SUSARs) are defined as SAEs that do not meet determination of expectedness as determined in accordance with applicable product information (Investigator's Brochure or other reference documentation). Upon receipt of a SAE report from an Investigator site, all suspected adverse reactions related to the IMP which occur within the clinical trial will be assessed for expectedness. Any SAE not listed in the reference documentation is considered a Suspected Unexpected Serious Adverse Reaction (SUSAR). SUSARs will be reported by the Sponsor, or its designee, in compliance with local legal requirements. During the course of the study, the Sponsor will report within required timelines all SAEs that are both unexpected and at least reasonably related to the IMP (SUSARs) to the Health Authorities, IECs / IRBs as appropriate and to

ZX008 (Fenfluramine Hydrochloride)
ZX008-1601 Clinical Study PA 4.0 (Japan) 25 July 2022

the Investigators. This study will comply with all applicable regulatory requirements and adhere to the full requirements of ICH Topic E2A (Clinical Safety Data Management: Definitions and Standards for Expedited Reporting [1994]).

For the purpose of data collection in this study, a prolonged seizure or series of seizures from which the subject does not regain consciousness between ictal events, that is at least 30 minutes in duration, is termed status epilepticus (SE). SE should be entered as an SAE if a prolonged seizure or series of seizures persists for 30 minutes or longer, regardless of administration of rescue medication, *and* is either diagnosed by a medical professional or occurs more than once in a day. SE lasting for less than 30 minutes should be entered as an AE, unless one of the other SAE criteria (eg, hospitalization) are met. If this incident involves multiple seizures close in time, the SE definition applies if the seizures are close together such that consciousness is not regained between ictal events.

Adverse events that do not fall into the above categories are defined as nonserious AEs.

8.1.3 Adverse Events of Special Interest

As per ICH guidance (E2F Development Safety Update Report [2011]), the sponsor has identified the following AESIs for the ZX008 program (Table 16).

Table 16: Adverse Events of Special Interest

| |
|---|
| Metabolic/Endocrine |
| 1. Elevated prolactin level $\geq 2x$ above the upper limit of normal (ULN) |
| 2. Hypoglycemia – < 3.0 mmol/l or 54 mg/dl, whether that level is associated with symptoms or not |
| Neuropsychiatric |
| 1. Suicidal thoughts, ideation or gestures |

8.2 SEVERITY OF ADVERSE EVENTS

The severity of AEs (whether nonserious or serious AEs) is to be assessed by the investigator as follows (Table 17).

ZX008 (Fenfluramine Hydrochloride)
ZX008-1601 Clinical Study PA 4.0 (Japan) 25 July 2022

Table 17: Severity Definition of Adverse Events

| Severity | Definition |
|-----------|---|
| Mild: | A type of AE that is usually transient and may require only minimal treatment or therapeutic intervention. The event does not generally interfere with usual activities of daily living. |
| Moderate: | A type of AE that is usually alleviated with additional specific therapeutic intervention. The event interferes with usual activities of daily living, causing discomfort but poses no significant or permanent risk of harm to the research participant. |
| Severe: | A type of AE that interrupts usual activities of daily living, or significantly affects clinical status, or may require intensive therapeutic intervention. |

8.3 CAUSALITY OF ADVERSE EVENTS

The causal relationship of an AE to IMP must always be assessed by the investigator. All AEs will be classified as either **related** or **not related** to IMP. If a causality assessment is not provided for an AE (including an SAE), that AE will be considered as related to IMP.

The degree of certainty with which an AE is attributed to IMP or an alternative cause (eg, natural history of the underlying disease, concomitant medication) will be determined by how well the event can be understood in terms of:

- Known pharmacology of ZX008
- Clinically and/or pathophysiologically plausible context
- Reaction of a similar nature previously observed with similar products, or reported in the literature for similar products as being product related (eg, headache, facial flushing, pallor)
- Plausibility supported by the temporal relationship (eg, the event being related by time to administration or termination of treatment with IMP drug withdrawal or reproduced on rechallenge)

The following classifications should be used in categorization of relatedness:

Not Related: Concomitant illness, accident or event with no reasonable association with study drug.

Related: The event follows a reasonable temporal sequence from administration of study drug and is definitive pharmacologically; cannot to be attributed to concurrent disease or other factors or medications. A clinically reasonable response should be observed if the study drug is withdrawn or dose reduced.

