1. Subject is male or non-pregnant, non-lactating female, age 2 to 35 years, inclusive as of the day of the Screening Visit. Female subjects of childbearing potential must not be pregnant or breast-feeding. Female subjects of childbearing potential must have a negative urine or serum pregnancy test at screening. Subjects of childbearing or child-fathering potential must be willing to use medically acceptable forms of birth control (see [Section 4.4](#)), which includes abstinence, while being treated on this study and for 90 days after the last dose of study drug.
2. Subject must have a diagnosis of Lennox-Gastaut syndrome, where seizures that result in drops are not completely controlled by current antiepileptic treatments. (Subjects without a formal diagnosis may still be enrolled after review and consultation between the Investigator and Sponsor, and in some cases, the Epilepsy Study Consortium. Final decisions on enrollment are at the discretion of the sponsor if all other criteria are met.)
3. Subjects must meet all of the following 4 criteria for Lennox-Gastaut syndrome, as defined in this protocol:
 - a. Onset of seizures at 11 years of age or younger.

ZX008 (Fenfluramine Hydrochloride)**ZX008-1601 Clinical Study PA 4.0 (Japan) 25 July 2022**

- b. Multiple seizure types (must include TS or TA), including countable motor seizures that result in drops. Countable motor seizure types eligible for inclusion are: GTC, TS, CS, AS, FS with observable motor symptoms, and MS with a drop.
 - c. Abnormal cognitive development.
 - d. Evidence of EEG in the medical history that shows abnormal background activity accompanied by slow spike and wave pattern <2.5 Hz. (Acceptable evidence includes a copy of the EEG trace, EEG report, or physician note that appropriately describes the EEG findings.)
4. Subject must have had at least 8 drop seizures in the last 4 weeks prior to Screening (minimum of 4 drop seizures in the first two weeks and 4 in the last two weeks before Screening), by parent/guardian report to investigator or investigator medical notes
 5. Receiving at least 1 concomitant AED and up to 4 concomitant AEDs, inclusive. KD and VNS are permitted but do not count towards the total number of AEDs. Rescue medications for seizures are not counted towards the total number of AEDs.

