ZX008 was generally well tolerated in both Study 1 and Study 1504 Cohort 2. Though more subjects randomized to ZX008 than to placebo reported TEAEs during the double-blind studies, the percent of subjects with serious TEAEs was similar. Additionally, the adverse events observed in the program were either already known to be associated with fenfluramine, are common to many other antiepileptic drugs being prescribed to these patients, and/or are common to the age group and population studied. Specifically, the most common adverse events seen were diarrhea, fatigue, pyrexia, upper respiratory tract infection, blood glucose decreased, weight decreased, decreased appetite, lethargy and tremor. No valvular heart disease, pulmonary arterial hypertension or abnormal valve structure was observed in any subject at any time during the entire program.

ZX008 (Fenfluramine Hydrochloride)
ZX008-1601 Clinical Study PA 4.0 (Japan) 25 July 2022

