8.7 REPORTING OF SERIOUS ADVERSE EVENTS BY INVESTIGATOR TO IEC/IRB

The timeframe within an IEC/IRB must be notified of a death or an unexpected SAE considered at least possibly related to the IMP is stipulated by each individual IEC/IRB. The investigator is responsible for complying with the requirements for IEC/IRB notification. The investigator will notify the relevant IEC/IRB within the applicable timeframe by forwarding the

ZX008 (Fenfluramine Hydrochloride)
ZX008-1601 Clinical Study PA 4.0 (Japan) 25 July 2022

safety report (eg, MedWatch/CIOMS form) completed by the sponsor/designee for the notifiable event.

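### Section 8.3's two mandatory causality classes leave a gap, and the Related class sets a stricter bar than the reporting rules in Sections 8.1.2 and 8.7

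*Protocol*

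**What the plan says.** Protocol Section 8.3 has the investigator assess causality for every adverse event in two classes, introduced by "The following classifications should be used in categorization of relatedness". Related needs a reasonable time sequence and an event that "is definitive pharmacologically; cannot to be attributed to concurrent disease or other factors or medications". It adds that a response to stopping or reducing the drug should be seen. Not Related is "Concomitant illness, accident or event with no reasonable association with study drug". The section also lists plausibility factors for judging the degree of certainty (pharmacology, clinical context, similar products, timing). It supplies a default: "If a causality assessment is not provided for an AE (including an SAE), that AE will be considered as related to IMP".

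Two other sections act on relatedness in different terms. In Section 8.1.2 the sponsor reports "all SAEs that are both unexpected and at least reasonably related to the IMP". Section 8.7 covers notification to the ethics committee of a death or "an unexpected SAE considered at least possibly related to the IMP".

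For serious events that start after the observation period, Section 8.4 requires a report if a link to the product is conceivable, whatever the investigator's causality opinion, and points to Section 8.6. The matching sentence in Section 8.6 covers late events that are judged causally related.

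Sections 10.1.6.2 and 10.2.4.1 plan summaries of adverse events by relationship to study drug for Part 1 and Part 2.

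**The concern.** A two-class scheme works only if each event belongs in exactly one class. Here Related is written as near-certain causation and Not Related as the absence of any reasonable link. Everything between the two is left without a home.

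That middle ground should be well populated in this trial. Subjects must meet the protocol's LGS criteria, and inclusion criterion 5 reads "Receiving at least 1 concomitant AED and up to 4 concomitant AEDs, inclusive". Section 1.3 says that some of the events seen earlier in the programme "are common to many other antiepileptic drugs being prescribed to these patients". A competing explanation will often be available.

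Two things are at stake. First, the relatedness tables: Part 2 has safety as its primary objective, has no control arm, and may run to 72 months, so there is no concurrent placebo rate against which to read a related-event count. Second, expedited reporting: the rating that the investigator is told to make does not answer the question that 8.1.2 and 8.7 ask.

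**Working it through.** No power, sample-size or event figure is involved, so the check is a comparison of texts.

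**Step 1. Are the two classes exhaustive?** Take three kinds of event and apply both definitions in Section 8.3.

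| Event | Meets Related? | Meets Not Related? |
|---|---|---|
| Clear pharmacological link to ZX008, no other explanation | Yes | No |
| No reasonable link to ZX008 | No | Yes |
| Reasonable link to ZX008, and also attributable to LGS or an AED | No: attribution to disease or other medication excludes it | No: a reasonable association exists |

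The third row has no class. The plausibility factors in 8.3 speak of degrees of certainty, but there is no intermediate class in which to record one.

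**Step 2. Do the sections share a threshold?**

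| Section | Use | Bar |
|---|---|---|
| 8.3 | Investigator's rating | Definitive link, no attribution elsewhere |
| 8.1.2 | Sponsor's SUSAR reporting | At least reasonable |
| 8.7 | Ethics committee notification | At least possible |

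There are three different bars, and 8.3, the only place where relatedness is defined, has the highest. Section 8.1.2 is also not of one mind. It sends reactions related to the product to an expectedness assessment, which makes relatedness a gate. It then calls any unlisted serious event a SUSAR, which does not.

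**Step 3. Where would gap events be counted?** An investigator who follows the Related definition literally moves them to Not Related, and the related count falls. One who follows the Not Related definition literally moves them to Related. The text settles neither, so the count depends on which sentence each investigator reads as controlling.

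**Step 4. Can the size be derived?** Section 1.3 gives related treatment-emergent events for the earlier Dravet double-blind studies. The denominators follow from the all-event counts: 117 / 0.959 = 122 on ZX008 and 68 / 0.810 = 84 on placebo. Then 76 / 122 = 62.3% and 22 / 84 = 26.2%, as stated. The causality definition used in those studies is not given, so these rates cannot be turned into a fraction lost under 8.3.

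**Step 5. Late serious events.** Section 8.4 makes the duty independent of the investigator's causality judgement; the sentence in 8.6 to which it leads rests on that judgement. A site that works from 8.6 with the 8.3 definition could leave unreported an event that 8.4 requires.

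**The case against.** A reader might infer that hardly any event in this population could be rated Related, that related events will certainly be under-counted, and that SUSARs will be lost. The documents do not support that.

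- Gap events fail Not Related as well, so the direction of the error is not fixed by the text.
- Section 8.3 counts a missing assessment as related, and its plausibility factors are softer than the class definition.
- Under Section 8.6 every serious event during the study goes to the sponsor or Medical Monitor within 24 hours, whatever its causality. The sponsor then applies the lower bar in 8.1.2. Nothing says that the investigator's 8.3 rating alone decides expedited reporting.
- The sentence in Section 1.3 about events shared with other AEDs also names events already known for fenfluramine, which favours a Related rating.
- The Dravet rates of 62.3% and 26.2% give no support for the idea that almost nothing is rated Related.
- Adverse events are also tabulated regardless of causality, so the Part 1 comparison with placebo does not rest on attribution.
- Sections 8.4 and 8.6 can be read together: 8.6 does not say that only causally related late events are reportable.

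All of this limits the consequence, and most of it stands. It does not make the two classes exhaustive or give the three sections one threshold. The harmonising reading of 8.4 and 8.6 is possible, but a site has to supply it. The rule that all serious events are reported covers events during the study, so it does not settle the late ones.

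**Conclusion.** The point holds as a defect of definition and consistency. Section 8.3's mandatory classes are not exhaustive, and its bar for Related contradicts those in 8.1.2 and 8.7. The result is a risk, in both parts, of relatedness summaries that are too low or inconsistent between investigators. There is also a conditional risk of missed SUSARs, which arises only if the 8.3 rating is what drives the expedited-reporting decision. The mismatch between 8.4 and 8.6 on late serious events is real and belongs in the same correction.

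The size is unknown and cannot be computed from the protocol. The conclusion assumes that investigators apply the 8.3 wording as printed; the eCRF, the SAE form and site guidance are not shown and could soften or worsen the effect. Efficacy results and all-causality adverse event tables are unaffected.

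**What to change.** In Section 8.3, define Related as a reasonable possibility that the product caused or contributed to the event, even if disease or another medication may also have contributed. Define Not Related as no reasonable possibility. The two classes are then complementary.

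Use that one threshold, in the same words, in Sections 8.1.2, 8.3 and 8.7. In Section 8.1.2, reconcile the sentence that treats any unlisted serious event as a SUSAR with the sentences that condition on relatedness.

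Make Sections 8.4 and 8.6 agree on whether the investigator's causality judgement is a condition for reporting serious events that start after the observation period.

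The cost is protocol wording, an update to the CRF completion guidelines and a reminder to sites, with no added procedure or visit. The downside is a somewhat higher stated rate of related adverse events in all arms. Ratings already made under the present wording may not be comparable with later ones, so the study report should state when the definition changed.
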